## **2.3 SECONDARY ENDPOINTS**

The secondary endpoints will provide:

1. The occurrence of procedure-related MAEs reported as percentage of subjects with MAE, at 30-days, 9-months, 12-months, 24-months, and 36-months.  
Inclusive of:
  - a. Procedure-or device-related occurrence of death
  - b. Q-Wave MI
  - c. Clinically driven TLR
  - d. Significant embolic events
    - i. Defined as unanticipated kidney/bowel infarct clinically driven by symptoms of abdominal or back pain and confirmed with CT scan or open surgery, lower extremity ulceration or gangrene, or kidney failure after 30-days, 9-months, 12-months, 24-months, and 36-months.
2. Technical success defined as successful delivery and deployment of the iCAST™ RX Stent System with  $\leq 30\%$  residual angiographic stenosis after covered stent deployment (including post-dilatation) assessed via QVA by an independent core laboratory.
3. Procedural success defined as technical success without the occurrence of MAE prior to hospital discharge.
4. TLR measured as the proportion of subjects that require a clinically-driven reintervention of the target lesion through 9-months.
  - a. A clinically-driven TLR is defined as a TLR (PTA, bare metal stent or repeat covered stent deployment, or surgical bypass) due to documented recurrent hypertension from 30-days post-procedure level and/or deterioration in renal function from baseline value, associated with angiographic core laboratory adjudication of a  $\geq 60\%$  diameter covered stent restenosis.
5. Rate of incidental TLR defined as rate of TLRs not meeting the definition of a

clinically driven TLR.

6. Improved SBP control assessed at 30-days, 9-months, 12-months, 24-months and 36-months.
7. Secondary patency rate at 9-months after a clinically-driven TLR which restores patency after total occlusion.
8. Change in number and dosage of anti-hypertensive medications as compared to baseline.
9. Renal function compared to baseline as measured by eGFR at 30-days and 9-months.

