**Table 6: Potential AEs Related to Stent Placement**

Adverse Event	Anticipated Incidence
Abdominal Pain	< 0.1%
Abscess	< 0.1%
Acute or sub-acute thrombosis	< 0.1%
Acute myocardial infarction	< 0.1%
Allergic reaction to stainless steel, drugs, contrast agent, or anti-platelet agents	< 0.1%
Aneurysm	< 2%
Arrhythmias, including VF and VT	< 0.1%
Arteriovenous (AV) fistula	< 2%
Bowel infarct	< 1%
Death	< 6%
Dialysis	< 5%
Emboli (air, tissue, or thrombotic) resulting in tissue ischemia or infarction	< 4%
Emergency surgery to correct vascular complications	< 3%
Extremity ischemia/amputation	< 0.1%
Fever	< 0.1%
Hemorrhage	< 5%
Hematoma	< 4%
Hypotension or hypertension	< 17%
Inadequate implantation or Intimal trauma	< 5%
Inadvertent exclusion of branch or accessory vessel	< 10%
Incision site pain or infection	< 0.1%
Injury, dissection, perforation, or rupture of the vessel	< 2%
Kidney infarct	< 0.1%
Myocardial infarction or ischemia	< 1%
Nephrectomy	< 2%
Pseudo-aneurysm formation	< 1%
Pyrogenic reaction	< 0.1%
Renal insufficiency or failure	< 6%
Restenosis of stented lesion	< 21%
Sepsis/infection	< 0.1%
Stent embolization	< 0.1%
Stent migration/stent misplacement	< 1%
Stroke or other cerebrovascular accident	< 2%
Thromboembolic event	< 1 %
Tissue necrosis or ulceration	< 0.1%
Total occlusion	< 2%
Vessel spasm	< 0.1%

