Q-WAVE MYOCARDIAL INFARCTION	The diagnosis of MI will be made on the basis of clinical information available from hospitalization (discharge summaries, laboratory data, ECG) and will require an appropriate clinical history consistent with acute MI.

PATENCY	Defined and categorized as:  Primary : continuous patency without the occurrence of a total occlusion of the original lesion, without a re-intervention to treat a partial or total occlusion of the stented segment, or bypass of the stented segment due to clinically-driven restenosis or occlusion.  Secondary : any procedure that restores patency after occlusion.
PERFORATION	The complete penetration of the wall of renal artery; this specifically refers to accidental or pathologic perforation, rather than intentional penetration during surgery.
PRIMARY STENTING	Stent placement without prior PTCA, an initial attempt at balloon dilatation, or after intentionally undersized pre-dilatation solely for the purpose of facilitating stent positioning.
PROCEDURAL SUCCESS	Technical success without the occurrence of MAE prior to hospital discharge.
RESISTANT HYPERTENSION	Failure to achieve goal BP (or SBP $\geq$ 155mmHg) in patients who are adhering to full doses of $\geq$ 3 anti-hypertensive medications from at least 3 classes of drugs, one of which must be a diuretic.
RESTENOSIS	Recurrent stenosis $\geq$ 60% diameter luminal narrowing or recurrent translesional gradient, observed post-procedure as determined by the core laboratory. Restenosis is initially assessed by DUS and confirmation of percent diameter stenosis is made by a contrast angiography.
RESTENOTIC LESION	A lesion in the vessel segment that has undergone a prior percutaneous treatment.

SERIOUS ADVERSE EVENT	Any adverse experience that results in any of the following outcomes: 

• Death

• Is life-threatening

• Subject hospitalization or prolongation of existing hospitalization

• A persistent or significant disability or incapacity

• Congenital anomaly or birth defect

• Important medical events that may not be immediately life-threatening or result in death or hospitalization, but may jeopardize the subject or may require intervention to prevent one of the outcomes listed in the definition above.

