5.2 Discussion of Endpoint Determination

The primary functional endpoint of primary patency has been established since the clinical care

Amendment #1: 15Jul13

Confidential

of the physician is considered a more objective measurement of stent performance than the restenosis measurement of DUS alone. In standard practice, a DUS is used to determine patency of a stent. If a DUS is negative and the subject is asymptomatic, no intervention is typically conducted by a physician. If a subject is symptomatic or a DUS is positive, a confirmatory angiogram is typically performed to assess the patency of the vessel.

To properly match the functional outcomes with historical data, the endpoint will be calculated on a per lesion basis. This reflects the current standard of care of treating subjects with single vessel renal artery lesions and those subjects with bilateral renal artery stenosis. Analysis of past studies has demonstrated that the number of lesions treated per subject has increased with time. A recent renal trial reported 1.2 lesions per subject were treated.

The primary clinical endpoint of reduction in SBP has been established to determine the benefit of revascularization therapy to perfuse the kidney. The Framingham Heart Study showed that decreasing SBP by 10mmHg can be lifesaving. Additionally, Joint National Committee VII (JNC VII) estimates that a 5mmHg reduction in SBP would reduce the incidence of stroke in subjects by 14%, coronary heart disease (CHD) by 9%, and overall mortality by 7%. JNC VII also presented data from a UK diabetes study that demonstrated a 10mmHg decrease in SBP was associated with average reductions of 15% for diabetes-related mortality, 11% for MI, and 13% for microvascular complications of retinopathy or nephropathy.

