6. CHANGES IN THE CONDUCT OF THE STUDY OR PLANNED ANALYSES

6.1 Changes in the Conduct of the Study

The enrollment for Protocol/CIP No. iCAST™ RX-ARAS-001 has been terminated after 68 subjects were screened and enrolled in the study as of November 2017. Enrolled subjects will be followed up to study completion.

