A clinically-driven TLR is defined as a target lesion revascularization (PTA, bare metal stent or repeat covered stent deployment, or surgical bypass) due to documented recurrent hypertension from 30-days post-procedure level and/or deterioration in renal function from baseline value, and associated with angiographic core laboratory adjudication of a $\geq 60\%$ diameter covered stent restenosis.

The percentage of TLRs will be derived as the number of subject-lesions that require a clinically-driven re-intervention divided by the number of subject-lesions in the ITT population.

5. Rate of incidental TLR

The rate of TLRs not meeting the definition of a clinically-driven TLR will be derived as the number of observed non-clinically driven TLRs divided by the total number of subject-lesions in the ITT population.

6. Improved SBP control assessed at 30-days, 9-months, 12-months, 24-months and 36-months.

The change from baseline in systolic blood pressure (SBP) at each follow-up time point will be computed as follows:

$$\text{SBP change from baseline} = (\text{SBP value at follow-up} - \text{SBP value at baseline})$$

7. Secondary patency rate at 9-months

Secondary patency rate at 9-months after a clinically-driven TLR which restores patency after total occlusion. For each subject-lesion, an indicator variable will be derived which identifies if the lesion meets secondary patency. The incidence of secondary of patency at 9 months will be computed as the number of subject-lesions that met secondary patency divided by the number of subject-lesions for the ITT population.

Confidential

8. Change in number and dosage of anti-hypertensive medications

Anti-hypertensive medications as well as the dosage will be recorded at baseline and throughout the study follow-up. The total number of anti-hypertensive medications will be computed as the sum of all available anti-hypertensive medications at each time point. Change from baseline will be computed as follows:

Change from baseline in the number of antihypertensive medications = (number of anti-hypertensive medications at follow-up – the number of anti-hypertensive medications at baseline)

Additionally, an indicator variable which detects if an increase in the number of antihypertensive medications (change from baseline > 0) was observed will be derived.

Similarly, the change from baseline in the anti-hypertensive medication dosage (within the same medication) will be computed as follows:

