9.3 Analysis Population

Intent-to-Treat (ITT) Analysis Population: All subjects enrolled in the study will be included in the ITT analysis population. This will be the primary analysis population.

Per Protocol (PP) Analysis Population: All subjects enrolled in the study, who receive the study device as intended with no major protocol deviations will be included in the per protocol analysis population.

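### Secondary patency counts only lesions re-opened after total occlusion but divides by every ITT lesion, so the reported figure cannot be read as a patency rate

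*SAP*

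**What the plan says.** **Numerator.** Protocol 2.3 item 7 gives the endpoint as "Secondary patency rate at 9-months after a clinically-driven TLR which restores patency after total occlusion", and SAP 7.6.2 item 7 repeats it. Protocol Appendix 2 defines secondary patency more loosely, as "any procedure that restores patency after occlusion". All three require a prior occlusion. The Appendix 2 wording does not require the procedure to be a clinically driven TLR, or the occlusion to be total.

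**Indicator.** SAP 7.6.2 adds: "For each subject-lesion, an indicator variable will be derived which identifies if the lesion meets secondary patency". It gives no separate code for lesions that are still primarily patent.

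**Denominator.** The SAP divides "the number of subject-lesions that met secondary patency divided by the number of subject-lesions for the ITT population". SAP 9.3 states: "All subjects enrolled in the study will be included in the ITT analysis population". The denominator is therefore every lesion of every enrolled subject, occluded or not. The Protocol gives no denominator.

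**Status.** SAP 9.10.3 lists the endpoint among those summarized descriptively, without a hypothesis test.

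**The concern.** The numerator and denominator describe different sets of lesions. Only a lesion that has occluded can enter the numerator, while a lesion that stays open throughout adds to the denominator alone. A table headed secondary patency would then show a percentage near zero next to a primary patency rate that SAP 5.5 assumes to be 82%. A reader would expect secondary patency to be at least as high as primary patency, since it normally adds the rescued lesions to those that never failed. The figure also cannot separate a device that never occluded from one whose occlusions were never re-opened. After early termination the SAP treats all inferential results as descriptive, so the printed rates are the trial's main output and should mean what their labels say.

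**Working it through.** Neither document states an expected secondary patency rate, so there is no planned figure to reproduce. The check is algebra, followed by an illustration.

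**Notation.** L = all ITT lesions; O = lesions that totally occluded; R = occluded lesions re-opened by a clinically driven TLR.

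**The cap.** The SAP rate is R/L. Since R ≤ O, R/L ≤ O/L. This holds for any L. If O = 0 the rate is 0; if O > 0 and R = 0 the rate is also 0. Strictly the cap is tighter still, because R cannot exceed the occluded lesions that received a clinically driven TLR.

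**Inputs for the illustration**
- Subjects: SAP 6.1 says enrollment "has been terminated after 68 subjects were screened and enrolled in the study as of November 2017".
- Lesions per subject: SAP 5.2 notes that "A recent renal trial reported 1.2 lesions per subject were treated". That is another trial, so 1.0 to 1.2 is an assumption here. L runs from 68 × 1.0 = 68 to 68 × 1.2 = 81.6, about 82.
- Occlusion rate: Protocol Table 6 anticipates a total-occlusion incidence below 2%. It gives no time frame and no per-lesion basis, so 2% per lesion at 9 months is an assumption.

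**Expected occlusions and chance of none** (lesions treated as independent)
- At 2%: 68 × 0.02 = 1.36 and 82 × 0.02 = 1.64 expected occlusions. Chance of none: 0.98^68 = 0.253 and 0.98^82 = 0.191.
- At 1%: chance of none is 0.99^68 = 0.505 and 0.99^82 = 0.439.

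With no occlusions the SAP rule must print 0%.

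**Scenarios with L = 82.** The last column assumes that every lesion that did not occlude is open at 9 months, including any retreated for partial occlusion.

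| Occluded (O) | Re-opened (R) | SAP rule R/L | R/O | All open (L − O + R)/L |
|---|---|---|---|---|
| 0 | 0 | 0.0% | undefined | 100.0% |
| 2 | 0 | 0.0% | 0% | 97.6% |
| 2 | 2 | 2.4% | 100% | 100.0% |
| 4 | 0 | 0.0% | 0% | 95.1% |
| 4 | 4 | 4.9% | 100% | 100.0% |

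The first and fourth rows are very different results, yet both print 0.0% under the SAP rule.

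**A check on the repair.** Under Protocol 2.2 and SAP 7.6.1, primary patency is also lost by re-intervention for a partial occlusion. A cumulative numerator built only from primary patent lesions plus re-opened total occlusions would therefore count a lesion retreated for partial occlusion, and open at 9 months, as a failure. For scale, borrow the 8.5% subject-level TLR average in Protocol Table 4 as an assumed lesion-level rate of such retreatment: 82 × 0.085 ≈ 7 lesions, and (82 − 7)/82 = 91.5% although all 82 are open. The numerator must include these lesions.

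**The case against.** The strongest reply is that the SAP does not spell out the indicator for a primarily patent lesion. If the sponsor meant a cumulative measure, the all-lesion denominator is correct and only the numerator text is loose. That intention is possible but not written. Every definition requires a prior occlusion, so a programmer following SAP 7.6.2 would code a never-occluded lesion as not meeting secondary patency. On either reading the text has to change.

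A second reply is that the quantity can be understood as an incidence of restorations per treated lesion. That is true, but it is then not a patency rate and should not carry that name.

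A third reply is that the consequence is small. The endpoint is descriptive, counts accompany percentages, and SAP 9.11.10 and 9.11.11 plan lesion-level angiographic and revascularization listings, from which a careful reader could reconstruct much of what happened. This stands and limits the weight of the point. It does not make the headline percentage interpretable.

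Two stronger readings may tempt a reader. One is that the measure is reversed, so that better devices always score lower. The scenarios do not support that: zero occlusions and four unrepaired occlusions give the same 0.0%, so the figure is mainly uninformative rather than consistently inverted. The other is that the reported rate must lie between 0% and 2.4%, that is, 0 to 2 of 82. That is not a bound. Table 6 gives no time frame or lesion basis, 1.2 lesions per subject is borrowed, and at a true 2% the chance of three or more occlusions in 82 lesions is about 23%.

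**Conclusion.** The point holds. As written, SAP 7.6.2 item 7 yields re-opened lesions over all lesions, a figure capped by the total-occlusion rate and equal to 0% both when nothing occludes and when nothing is re-opened. This follows from the stated definition and formula and needs no assumption about lesion count or event rate. The illustrative figures (1.4 to 1.6 expected occlusions, and a 19% to 25% chance of a forced 0%) rest on 68 to 82 lesions, a 2% occlusion rate per lesion by 9 months, and independence between lesions. The damage is confined to one descriptive secondary endpoint. No sample size, performance goal, test or primary conclusion depends on it, and it is speculation to say that readers would take the figure as poor device performance. It should be corrected before the tables are produced.

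**What to change.** State one matched pair in SAP 7.6.2 item 7.

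- **(a) Cumulative secondary patency.** Numerator: all lesions open at 9 months, namely those primarily patent, those re-opened after total occlusion, and those retreated for partial occlusion and open. Denominator: all ITT lesions with known 9-month status, with the number of unknown status shown alongside.
- **(b) Restoration after occlusion.** Numerator: re-opened lesions. Denominator: totally occluded lesions. Use that label instead of secondary patency, show counts, and print not estimable if none occlude. With only one or two occlusions a percentage would say little.

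Option (a) can be compared with primary patency; option (b) answers the narrower question that the current definition asks. In either case, reconcile Protocol Appendix 2, which accepts any restoring procedure, with Protocol 2.3 and SAP 7.6.2, which require a clinically driven TLR after total occlusion.

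The cost is a short SAP revision, one changed derivation and a relabelled table row. The 9-month duplex ultrasound, follow-up angiography and revascularization records are already planned, so no new data collection is needed. Option (a) also requires a stated rule for lesions of unknown status.

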	
Eligible subjects will undergo a two-week Medical Documentation Screening period to confirm resistant hypertension (SBP <math>\geq</math> 155mmHg) while on maximum tolerable doses of <math>\geq</math> three anti-hypertensive medications from at least three classes of drugs, one of which must be a diuretic.
 
There must be documented clinical evidence to support likelihood of angiographic findings <math>> 80\%</math> whether it is Duplex Ultrasound (DUS), Computed Tomography angiogram (CTa), Magnetic Resonance angiogram (MRa) or other medical evidence. After meeting screening and clinical eligibility criteria, subjects will undergo a baseline assessment for angiographic eligibility. After angiographic documentation of a <math>\geq 80\%</math> diameter renal artery stenosis or Fraction Flow Reserve (FFR) <math>< 0.8</math> is confirmed, the subject may be enrolled in the trial by placement of the investigational device.
 
The 9-month visit will include a follow-up DUS of the target renal artery. If the DUS is non-diagnostic due to an imaging quality problem, such as overlying bowel gas or body habitus, a second DUS may be attempted. If the DUS is indicative of <math>\geq 60\%</math> stenosis as determined by the core laboratory, or the second DUS remains non-diagnostic, a contrast angiogram will be used to assess the degree of restenosis of the covered stent(s).
 
Clinical follow-up visits will be required for all enrolled subjects at 30-days, 9-months, 12-months, 24-months, and 36-months. A 6-month and 18-month visit will occur via telephone to collect medication usage and Adverse Events (AEs) only. The 36-month clinic office visit will be required as the final safety visit.

SUBJECT POPULATION	Subjects who are candidates for a renal artery revascularization with $\geq 80\%$ visual stenosis and have resistant hypertension with $\geq 155\text{mmHg}$ while on $\geq 3$ anti-hypertensive medications from at least 3 classes of drugs, one of which must be a diuretic.
NUMBER OF SUBJECTS	Up to 138 subjects will be enrolled in this trial.
ESTIMATED TRIAL DURATION	The trial duration is projected for 60 months.

ESTIMATED SUBJECT DURATION	Each subject is expected to be enrolled and followed for a total of 36 months.

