### 6.3 DOCUMENTATION

All AEs must be listed in the subject's source record, transcribed onto on the appropriate eCRF, and will be characterized by the following criteria:

- Intensity or Severity
- Relatedness
- Outcome
- Treatment or Action Taken
- Expectedness

All AEs (serious and non-serious) will be recorded upon completion of the ICF process through the 9-month follow-up visit. Thereafter, only SAEs (for example, those that result in hospitalization, permanent disability, death, or threat of death) will be recorded. All SAEs will be reported to the CEC and DSMB.

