## APPENDIX 4: SCHEDULE OF EVENTS

	(-14)-Days (Medical Documentation Screening period)  Prior to Procedure	(-7)-Days   Prior to Procedure	Day 0  Procedure	30-Days (+14/-7 Days)  Office Visit	6-Months (+/-30 Days)  Phone Call	9-Months (+/-30 Days)  Office Visit	12-Months (+/- 30 Days)  Office Visit	18-Months (+/-30 Days)  Phone Call	24-Months (+/- 60 Days)  Office Visit	36-Months (+/- 60 Days)  Office Visit
Informed Consent	X									
General Entry Criteria	X									
Angiographic Entry Criteria			X							
Demographics and Medical History	X									
Weight (Kg)/ Height (cm)	X									
Vital Signs	X		X	X		X	X		X	X
BP Assessment	X 	X 	X	X		X	X		X	X
Laboratory Assessments	X 		X 	X 		X 				
Test for Proteinuria	X 									
Physical Exam	X		X	X		X	X		X	X
Pregnancy Test	X 		X 							
iCAST™ RX Stent System Placement			X							
Duplex Ultrasound				X		X				
Angiography			X 			X 				
Concomitant Medications	X	X	X	X	X	X	X	X	X	X
Adverse Events	X	X	X	X	X	X	X	X	X	X

A minimum of two office visits are required within the 14-day Medical Documentation Screening period. If the procedure is scheduled > 14 days from the first office visit, subjects should return every two weeks (+/- 3 days) for BP assessments and monitoring.

Chem12 panel which includes: Glucose, Calcium, Albumin, Total protein, Sodium, Potassium, CO2, Chloride, BUN, creatinine, ALP, ALT, AST, and bilirubin.

Test for proteinuria should be completed for subjects during Step 2 of the Medical Documentation Screening Period.

Pregnancy test required at screening and on the day of procedure for females of childbearing potential only.

All subjects must have angiography to determine percent diameter stenosis prior to treatment and at 9-months (if DUS indicates ≥ 60% stenosis).

AE collection (serious and non-serious) will begin upon completion of the ICF process through the 9-month follow-up visit, thereafter only SAEs and UADEs will be recorded.

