7.1 Schedule of Evaluation

Table 2 SCHEDULE OF EVENTS

	(-14)-Days (Medical Documentation Screening period) ⁷ Prior to Procedure	(-7)-Days ⁷ Prior to Procedure	Day 0 Procedure	30-Days (+14/-7 Days) Office Visit	6-Months (+/-30 Days) Phone Call	9-Months (+/-30 Days) Office Visit	12-Months (+/- 30 Days) Office Visit	18-Months (+/-30 Days) Phone Call	24-Months (+/- 60 Days) Office Visit	36-Months (+/- 60 Days) Office Visit
Informed Consent	X									
General Entry Criteria	X									
Angiographic Entry Criteria			X							
Demographics and Medical History	X									
Weight (Kg)/ Height (cm)	X									
Vital Signs	X		X	X		X	X		X	X
BP Assessment¹	X ¹	X ¹	X	X		X	X		X	X
Laboratory Assessments²	X ²		X ²	X ²		X ²				
Test for Proteinuria³	X ³									
Physical Exam	X		X	X		X	X		X	X
Pregnancy Test⁴	X ⁴		X ⁴							
iCAST™ RX			X							

Confidential

	(-14)-Days (Medical Documentation Screening period) ⁷ Prior to Procedure	(-7)-Days ⁷ Prior to Procedure	Day 0 Procedure	30-Days (+14/-7 Days) Office Visit	6-Months (+/-30 Days) Phone Call	9-Months (+/-30 Days) Office Visit	12-Months (+/- 30 Days) Office Visit	18-Months (+/-30 Days) Phone Call	24-Months (+/- 60 Days) Office Visit	36-Months (+/- 60 Days) Office Visit
Stent System Placement										
Duplex Ultrasound				X		X				
Angiography⁵			X ⁵			X ⁵				
Concomitant Medications	X	X	X	X	X	X	X	X	X	X
Adverse Events⁶	X	X	X	X	X	X	X	X	X	X

¹A minimum of two office visits are required within the 14-day Medical Documentation Screening period. If the procedure is scheduled > 14 days from the first office visit, subjects should return every two weeks (+/- 3 days) for BP assessments and monitoring.

²Chem12 panel which includes: Glucose, Calcium, Albumin, Total protein, Sodium, Potassium, CO2, Chloride, BUN, creatinine, ALP, ALT, AST, and bilirubin.

³Test for proteinuria should be completed for subjects during Step 2 of the Medical Documentation Screening Period.

⁴Pregnancy test required at screening and on the day of procedure for females of childbearing potential only.

⁵ All subjects must have angiography to determine percent diameter stenosis prior to treatment and at 9-months (if DUS indicates $\geq 60\%$ stenosis).

⁶AE collection (serious and non-serious) will begin upon completion of the ICF process through the 9-month follow-up visit, thereafter only SAEs and UADEs will be recorded.

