Change from baseline in the antihypertensive medication dosage = (Dosage of anti-hypertensive medication at follow-up – the dosage of the anti-hypertensive medication at baseline).

An indicator variable which identifies any increases in dosage (change from baseline > 0) will also be derived.

9. Renal function compared to baseline as measured by eGFR at 30-days and 9-months.

Renal function will be assessed by eGFR at the 30-days and 9-months of study follow-up. eGFR results will be estimated by the abbreviated Modification of Diet in Renal Disease(MDRD) equation : $186 \times (\text{Creat} / 88.4) - 1.154 \times (\text{Age}) - 0.203 \times (0.742 \text{ if female}) \times (1.210 \text{ if black})$.

The change from baseline in eGFR will be computed as follows:

Change from baseline in eGFR = (eGFR result at follow-up – eGFR result at baseline)

- i. In addition, an indicator variable will be derived in order to identify decreases from baseline in eGFR of >25%, >40%, >50% at any time point.

Amendment #1: 15Jul13

7.6.3.Safety Outcomes and Other Parameters

The main safety outcome is the incidence of subjects with any adverse event experienced after the study procedure has occurred over the totality of the study.

Other parameters collected to monitor safety and/or to derive efficacy include:

- Vital signs (systolic and diastolic blood pressure)
- Laboratory Assessments (chemistry, urine analysis, proteinuria, eGFR)
- Physical Examination (assessment of general appearance, abdomen, cardiovascular, dermatologic, genitourinary, head, eyes, ear, nose and throat (HEENT), lymph nodes, musculoskeletal, neurological, respiratory)
- Duplex Ultrasound (degree of stenosis)
- Angiography (degree of stenosis)
- Revascularization (number of revascularization, location, type)
- Concomitant medications/antihypertensive medications
- Mortality

8. STATISTICAL METHODS**8.1 General Statistical Considerations**

Data collected in this study will be presented using summary tables and subject data listings.

Demographic, endpoint information, safety data and other parameters will be summarized and presented for the ITT and Per-Protocol populations accordingly. Summaries for continuous and ordinal variables will include the number of observations (n), arithmetic mean, standard deviation (SD), minimum (min), maximum (max), median, and 95% confidence intervals of the means.

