9.11.4. Anticipated Adverse Events

Based on the literature and on clinical and commercial experience with implantation of a covered stent in human arteries,

Table 4: Anticipated AEs, includes anticipated AEs that have been identified as possible complications:

Table 4: Anticipated AEs

 ○ Abdominal Pain ○ Abscess ○ Acute or sub-acute thrombosis ○ Acute myocardial infarction ○ Allergic reaction to stainless steel, drugs, contrast agent, or anti-platelet agents ○ Aneurysm ○ Arrhythmias, including Ventricular Fibrillation (VF) and Ventricular Tachycardia (VT) ○ Arteriovenous (AV) fistula ○ Bowel infarct ○ Death ○ Dialysis ○ Emboli (air, tissue, or thrombotic) resulting in tissue ischemia or infarction ○ Emergency surgery to correct vascular complications ○ Extremity ischemia/amputation ○ Fever ○ Hemorrhage ○ Hematoma 	
 ○ Hypotension or hypertension ○ Inadequate implantation or Intimal trauma ○ Inadvertent exclusion of branch or accessory vessel ○ Incision site pain or infection ○ Injury, dissection, perforation, or rupture of the vessel ○ Kidney infarct ○ Myocardial infarction or ischemia ○ Nephrectomy ○ Pseudo-aneurysm formation ○ Pyrogenic reaction ○ Renal insufficiency or failure ○ Restenosis of stented lesion ○ Sepsis/infection ○ Stent embolization ○ Stent migration/stent misplacement ○ Stroke or other cerebrovascular accident ○ Thromboembolic event ○ Tissue necrosis or ulceration ○ Total occlusion ○ Vessel spasm
---	--

The study main safety outcome is the incidence of subjects with any adverse event

Amendment #1: 15Jul13

Confidential

observed after the study procedure over the totality of the study. An overall summary that includes the incidence of subjects with any adverse event during the entire study, the number of AEs and the number and percentage of subjects who experienced at least one AE will be presented. This summary will also include all AEs, serious AEs (SAEs), unanticipated adverse device effects (UADE), procedure-related AEs, procedure related SAEs and AEs with outcome of death.

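### The main safety outcome counts any adverse event over the whole study, but non-serious events are recorded only to the 9-month visit of a 36-month follow-up

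*SAP*

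**What the plan says.** **Outcome.** SAP 7.6.3 sets the main safety outcome as the incidence of subjects with "any adverse event experienced after the study procedure has occurred over the totality of the study". SAP 9.11.4 repeats it: "The study main safety outcome is the incidence of subjects with any adverse event" that is "observed after the study procedure over the totality of the study". Neither place limits it by seriousness or by time. The Protocol Summary gives the length of the study: "Each subject is expected to be enrolled and followed for a total of 36 months". SAP 6.1 confirms that follow-up continues to completion for the 68 subjects enrolled before enrollment stopped.

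**Recording.** Protocol 6.3 states: "All AEs (serious and non-serious) will be recorded upon completion of the ICF process through the 9-month follow-up visit". It continues: "Thereafter, only SAEs (for example, those that result in hospitalization, permanent disability, death, or threat of death) will be recorded". Footnote 6 of the schedule in Protocol Appendix 4 has all AEs collected "through the 9-month follow-up visit, thereafter only SAEs and UADEs will be recorded". Footnote 6 of the SAP's own schedule (7.1) agrees: "thereafter only SAEs and UADEs will be recorded".

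**Tables.** SAP 9.11.4 plans summaries by System Organ Class and Preferred Term for AEs, procedure-related AEs, UADEs, SAEs, serious procedure-related AEs and fatal AEs. They are split into before and after the procedure. No split or label marks the change in recording at month 9.

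**The concern.** The SAP carries the recording limit in its schedule but does not apply it to the outcome or the AE tables. The reported rate would therefore combine two regimes under one label: every AE up to the 9-month visit, and only serious ones (with UADEs) from then to month 36. The label would claim coverage of non-serious events over 36 months that the data cannot support.

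With all inference now descriptive (SAP 2 and 6.2), the rate and its label are the whole result. Someone reading the final table could take a low frequency of a late-onset, mostly non-serious term as a finding when such events were simply not collected.

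**Working it through.** The documents give no expected any-AE rate, so there is no planned figure to reproduce. The check sets the definition against the recording period and then illustrates the possible size.

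**1. Share of follow-up with full recording.** By months: 9/36 = 25%. By the target days in SAP 7.4: 273/1095 = 24.9%, ranging from 243/1095 = 22.2% to 303/1095 = 27.7% across the 9-month window. Non-serious events therefore go unrecorded for about 75% of planned follow-up time.

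**2. Who is misclassified.** The outcome is per subject. A subject is wrongly counted as AE-free only if all three of these hold:
- no post-procedure AE is recorded by the 9-month visit;
- no SAE or UADE occurs later;
- at least one non-serious AE occurs later.

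Such subjects can only be removed from the numerator, so the direction of this mechanism is fixed.

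**3. Which tables are affected.** The all-AE and procedure-related-AE tables include non-serious events and are affected. The SAE, serious procedure-related and fatal-AE tables are not, because SAEs are recorded throughout. The UADE table is not affected under footnote 6.

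**4. Illustrative size.** Let I be the share of subjects with an AE by month 9, and f the share of the AE hazard that is serious. Both are assumptions; the documents give neither. With a constant hazard and complete 36-month follow-up, the period after month 9 is three times as long as the one before it, so:
- true 36-month rate = 1 − (1 − I)^4
- recorded rate = 1 − (1 − I)^(1 + 3f)

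Example with I = 0.5 and f = 0.1: true 1 − 0.5^4 = 93.8%; recorded 1 − 0.5^1.3 = 59.4%; shortfall 34.4 points, and 0.344 × 68 = 23.4 subjects.

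| I | True rate | Recorded, f = 0.1 | Recorded, f = 0.5 | Shortfall (points) | Subjects of 68 |
|---|---|---|---|---|---|
| 50% | 93.8% | 59.4% | 82.3% | 11.4 to 34.4 | 7.8 to 23.4 |
| 70% | 99.2% | 79.1% | 95.1% | 4.1 to 20.1 | 2.8 to 13.7 |
| 90% | 100.0% | 95.0% | 99.7% | 0.3 to 5.0 | 0.2 to 3.4 |

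**5. Lower hazard after month 9.** If the later hazard is one quarter of the earlier one, the exponents become 1.75 (true) and 1 + 0.75f (recorded). The shortfall is then 8.8 to 17.7 points for I = 50%, 6.9 to 15.2 for I = 70%, and 2.4 to 6.6 for I = 90%. Front-loading shrinks the error mainly by raising I. At a fixed I of 90%, a lower late hazard slightly enlarges it, because fewer of the remaining subjects have a later SAE that would count them.

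**The case against.** **It is a labelling matter, and the limit is disclosed.** Stopping non-serious AE recording at month 9 is a stated design choice, and the SAP's schedule shows it. That is fair: the recording rule is not the fault. But the outcome definition and the table plan do not carry the limit, so the outputs would be mislabelled if the SAP is followed.

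**The any-AE rate is not the principal safety evidence.** The protocol assesses safety through primary patency and through major adverse events reported from 30 days to 36 months; AEs come under other safety data (5.3.6.5). The any-AE rate has no hypothesis or performance goal. This stands and limits the consequence. The SAP nevertheless names it the main safety outcome.

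**Most subjects may have an AE by month 9.** This may well be so, and the headline error would then be a few points or less. It does not rescue individual terms that arise late and are mostly non-serious.

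**Later visits list AE collection.** The 12-, 18-, 24- and 36-month contacts (Protocol 4.5.4 to 4.5.7) list it without repeating the limit. Section 6.3 and both footnotes are explicit, so those lines do not restore full recording.

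**Stronger readings that do not hold.** A reader might infer three further things:
- *Every AE table is understated.* The separate SAE, UADE and fatal-AE summaries are already planned and are not touched.
- *Three quarters of AEs are lost.* The 75% is follow-up time, not events.
- *The reported rate is low on balance.* SAP 9.11.1 also counts as post-procedure an AE that began earlier but is ongoing, ends on or after the procedure date, or has no end date. That pushes the rate up. It is a separate issue, but it means the net direction is not settled by this point alone.

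**Conclusion.** The point holds: the main safety outcome as defined cannot be measured over 36 months with the data the protocol collects. Taken alone, the mechanism can only lower the any-AE rate and the all-AE and procedure-related-AE tables.

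Its size cannot be derived from the documents. The constant-hazard ranges (about 0.3 to 5, 4 to 20, and 11 to 34 points for month-9 shares of 90%, 70% and 50%) rest on assumed values of I, on f between 0.1 and 0.5, and on complete follow-up. They show that the error could be negligible or substantial; they do not estimate it. A summary cut at each subject's own 9-month visit would be free of it.

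The documents do not support reading this as a threat to the SAE, UADE or major-adverse-event results. It is an inconsistency in the definition and labelling of a named outcome, and worth correcting because the correction is cheap.

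**What to change.** - In SAP 7.6.3 and 9.11.4, define the main safety outcome as the incidence of subjects with any AE from the procedure through the 9-month visit.
- Keep the SAE and UADE summaries already planned, and state that they run through 36 months.
- Put the collection period in the title of every table that includes non-serious AEs (all AEs, procedure-related AEs, and the overall summary).
- Reconcile Protocol 6.3, which names only SAEs after month 9, with footnote 6 of both schedules, which names SAEs and UADEs.

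The cost is SAP wording, table titles and one protocol clarification. No new data, visits or analyses are needed.
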